2.2 Secondary Objectives

The secondary, exploratory objectives are to:

• Evaluate the association between the dose of inhaled tobramycin, plasma tobramycin pharmacokinetics, and peak tracheal aspirate tobramycin levels.

- Compare the change (pre vs. post study) in tracheal aspirate pathogenic bacterial colony forming unit (CFU) counts measured by high resolution culture, (1) between participants in the phase 1 trial and untreated infants in the observational cohort, and (2) between trial participants stratified by the administered dose of inhaled tobramycin.
- Compare the longitudinal change in measures of administered respiratory support (FiO₂, ventilator mean airway pressure, and respiratory severity score) during the 14-day study period, (1) between participants in the phase 1 trial and observational cohort and (2) between trial participants stratified by the administered dose of inhaled tobramycin.
- Compare changes (pre vs. post treatment) in tracheal aspirate cytokine levels, neutrophil/WBC ratio, and patterns in the airway microbiome, stratified by the administered dose of inhaled tobramycin.
- Change in the following measures of hypoxemia (SpO₂<80%): Intermittent hypoxemia (events lasting 10s-3min), prolonged hypoxemia (events lasting >1min), and daily proportion of time in hypoxemia
- Compare the longitudinal change in dynamic lung compliance, airway resistance, peak expiratory flow, and CO₂ elimination during the 14-day study period, (1) between participants in the observational cohort and phase 1 trial and (2) between trial participants stratified by the administered dose of inhaled tobramycin.

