5.1.4.3 Follow-up Phase

For the phase 1 trial participants, tracheal aspirate sampling will be performed for the following laboratory evaluations at two timepoints during the follow-up phase (\leq 48 hours after receiving the final dose of inhaled tobramycin and 14 days after receiving the final dose of inhaled tobramycin or on the day of planned tracheal extubation, if earlier):

- Tracheal aspirate cell count with differential
- Tracheal aspirate quantitative culture with antimicrobial sensitivities

For observational cohort participants, tracheal aspirate sampling for the above laboratory tests will be performed once during the follow-up phase, ≤48 hours after day 14 of the observation period.

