5.3 Efficacy Evaluations

Measures of potential drug efficacy will be assessed as secondary, exploratory endpoints. These will include the following outcomes:

• Change (pre vs post treatment) in tracheal aspirate pathogenic bacterial colony forming unit (CFU) counts measured by high resolution culture

Tracheal aspirates for high resolution culture will be obtained \leq 7 days prior to initiating inhaled tobramycin (as part of the screening procedures), \leq 48 hours after completing the final drug dose, and 14 days after completing the final drug dose (or on the day of planned tracheal extubation if earlier) (see schedule under section 4.3). For infants enrolled in the observational (non-treated) cohort, tracheal aspirate for culture will be obtained \leq 7 days prior to initiating the 14-day observation period (as part of the screening procedures) and \leq 48 hours after completing the observation period. These tests will be performed in the CHOP clinical laboratory as described in section 5.1.3.

Reduction in number and eradication of pathogenic GNR bacteria from the airways is anticipated to result in clinical benefit. Evidence from preterm infants with BPD indicates the presence of these organisms in the airway is associated with worse clinical outcomes.^{10,11} Moreover, data from children with CF demonstrate that early treatment of *P. aeruginosa* infection of the respiratory tract leads to improved clinical outcomes.^{16,88,89} As such, change in quantitative tracheal aspirate culture results following treatment with inhaled tobramycin is anticipated to be a suitable surrogate marker to assess the likelihood of clinical benefit. For this phase 1 feasibility trial, we will evaluate the relative intra-patient change in bacterial CFU counts and assess the association between the longitudinal change in CFU count, airway cytokine levels, and the RSS.

• Tracheal aspirate tobramycin levels

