6.3.3 Exploratory Secondary Safety and Efficacy Analyses

The exploratory secondary safety and efficacy endpoints listed in section 6.2 will be analyzed as described in **Table 7** (next page). In brief, all study data will first be summarized using standard descriptive statistics as appropriate based on data type and distribution. Assessments of change over time for all longitudinal secondary outcome data will first be assessed graphically, with and without stratification by the administered tobramycin dose. Next, paired t-tests or Wilcoxon sign rank tests will be used to compare

pre-trial baseline values to those recorded at later time points. Non-paired tests will be used to compare data baseline and subsequent data points between the infants in the phase 1 trial and observational (non-treated) cohorts.

	Values available for:			
Study outcome	Phase 1 trial cohort	Observational cohort	Statistical approach	
Secondary safety endpoints	Yes	Yes, for some endpoints	 Rates of the secondary tolerability endpoints will be summarized for each dose level. Descriptive, narrative details of these endpoints will also be provided as appropriate. Data on the rates of endotracheal tube obstruction, unplanned tracheal extubation, and audiology testing results will be compared between the trial and observational cohorts. Planned comparisons of audiology testing results are described in the Protection of Human Subjects document. 	
Secondary efficacy endpoints				
Negative TA culture for the target GNR	Yes	No	 Primary exploratory efficacy endpoint. Rates will be summarized for the trial cohort as a whole and stratified by drug dose level. 	
Change in TA GNR pathogen CFU	Yes	No	 Absolute (pre vs post) and relative change ([post trial – pre trial] / pre trial) in the target organism CFU/mL on the log₁₀ scale will be calculated for each phase 1 trial participant. Paired t-tests or Wilcoxon sign rank tests as appropriate will be used to compare pre- vs. post-trial absolute CFU/mL values for the whole cohort and stratified by drug dose level. 	
Tracheal aspirate tobramycin levels	Yes	No	 Values, stratified by drug dose, will be compared to established concentrations necessary to overcome the minimum inhibitory concentration needed to kill 90% of detected bacterial isolates (MIC₉₀).^{90,91} Values will also be used in our PK analyses. 	

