Tracheal aspirate cytokine levels	Yes	No	 Individual cytokine levels measured pre-trial, ≤48 hours after the final dose, and 14 days after the final drug dose will be summarized. Transformation (e.g. logarithmic) or categorization by centiles will be considered based on the data distribution. Correction for total protein levels in the tracheal aspirate will be employed to account for differences in dilution during sample collection. The relative intra-patient change for the individual cytokine levels 	
			 from pre-trial baseline to the 2 post-trial timepoints will be calculated and compared between dose levels. The association between change in cytokine levels and tobramycin dose will be explored using bivariate and multivariate correlation analyses with Bonferroni correction for multiple testing.¹⁰⁰ We will consider exploratory cluster and linear discriminate analyses to identify airway immunological profiles associated with differences in the response to inhaled tobramycin (e.g. change in CFU/mL).^{101,102} 	
Respiratory support measures Hypoxemia (SpO ₂ <80%)	Yes	Yes	 Continuously recorded FiO₂, MAP, and RSS values will be converted to time-weighted daily averages for each study day. Continuously recorded SpO₂ data will be used to calculate daily rates of intermittent and prolonged hypoxemia and daily total hypoxemia exposure. Assessment of longitudinal change using linear mixed effects models will be considered. 	
Pulmonary mechanics	Yes	Yes	 Infants in both study cohorts will undergo pulmonary mechanics measurements pre-trial, after 7d, and after 14d. Intra-patient change, relative to pre-trial baseline, will be calculated for each participant and compared (1) between the two cohorts and (2) stratified by drug dose. Assessment of longitudinal change using linear mixed effects models will be considered. 	

Table 7. Planned statistical techniques and data availability for the phase 1 trial outcomes

CFU, colony forming units; GNR, Gram-negative rod; TA, tracheal aspirate

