Lastly, hypothesis generating analyses will assess changes in bacterial CFU/mL (on the log₁₀ scale) as a function of: (1) the GNR organism cultured from the tracheal aspirate, (2) pre-trial airway cytokine levels, (3) pre-trial RSS, and (4) pre-trial pulmonary mechanics measurements. These data will help inform the selection of pre-specified subgroups group analyses that will be performed in future randomized trials.

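### The search for predictors of CFU change has no untreated contrast, so a purely prognostic factor cannot be told from a modifier of tobramycin's effect

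*Combined protocol and SAP*

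**What the plan says.** The last paragraph of section 6.3.3 states that "hypothesis generating analyses will assess changes in bacterial CFU/mL", on the log10 scale, in relation to four things: the organism cultured, pre-trial airway cytokines, pre-trial RSS and pre-trial pulmonary mechanics. It names no model, test, population, comparator or baseline-CFU term. It gives the purpose: "These data will help inform the selection of pre-specified subgroups group analyses that will be performed in future randomized trials".

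Table 7, in the same section, enters CFU change as Yes for the phase 1 cohort and No for the observational cohort, and says that the change "in the target organism CFU/mL on the log₁₀ scale will be calculated for each phase 1 trial participant". Its cytokine row, also phase 1 only, considers cluster and discriminant analyses to find "airway immunological profiles associated with differences in the response to inhaled tobramycin", with change in CFU/mL as the example of response.

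Other sections differ from the Table 7 entry. Section 2.2 and the synopsis list a comparison of CFU change "between participants in the phase 1 trial and untreated infants in the observational cohort". Section 5.3 says: "For infants enrolled in the observational (non-treated) cohort, tracheal aspirate for culture will be obtained" both before and after the observation period. Section 5.1.4.3 agrees: "For observational cohort participants, tracheal aspirate sampling for the above laboratory tests will be performed once during the follow-up phase", and those tests include quantitative culture. Table 7 itself lists respiratory support (which includes RSS) and mechanics as available in both cohorts.

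**The concern.** Colony counts in untreated infants also change over two weeks, and some pre-trial factors may predict how much. Suppose one organism tends to fall in count with or without tobramycin. In treated infants it will be associated with a larger fall, just as it would be if tobramycin worked better against it. Only a comparison with untreated infants carrying the same factor can separate the two, and the plan as tabulated leaves that comparison out. The result would then be described, in the words of the cytokine row, as response to the drug and carried into the choice of subgroups for later trials. This is a separate question from whether the average fall in CFU is overstated. It concerns which factors are put forward as modifiers.

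**Working it through.** **Stated figures.** The plan gives no power or error rate for these analyses. Its only power statement (section 6.4) concerns intermittent hypoxaemia. That statement reproduces and has no bearing here.

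**Inputs.**
- Treated infants: up to 24 (section 6.4), or 15 if each of the three lower doses needs only three infants and the 300 mg level has six (3 + 3 + 3 + 6).
- Untreated infants: 12 to 28 (section 6.4).
- Assumptions, because the documents give no values: a binary factor split about evenly; a shift in natural log10 CFU change of 0.5, 0.75 or 1.0 SD, equal in both cohorts; no modification of drug effect; two-sided 5% tests.

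**Step 1: treated-only test.** This is a two-sample t-test of CFU change by factor level, with noncentrality d × √(n₁n₂/(n₁+n₂)). The chance that a purely prognostic factor is flagged is:

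| Treated infants | d = 0.5 | d = 0.75 | d = 1.0 |
|---|---|---|---|
| 15 (7 v 8) | 15% | 27% | 43-44% |
| 24 (12 v 12) | 22% | 42% | 65% |

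**Step 2: cohort-by-factor contrast.** This is the factor difference in treated infants minus the factor difference in untreated infants. In simulation under the same assumptions it flags the factor about 5% of the time at 15 v 12, 24 v 12 and 24 v 28.

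**Step 3: precision of that contrast.** For an evenly split binary factor, the difference detectable with 80% power (normal approximation) is (1.960 + 0.842) × 2 × √(1/n_treated + 1/n_untreated):
- 15 v 12: 5.603 × √0.1500 = 2.2 SD
- 24 v 12: 5.603 × √0.1250 = 2.0 SD
- 24 v 28: 5.603 × √0.0774 = 1.6 SD

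**Step 4: does adjusting for baseline CFU settle it?** Take an assumed pre-post correlation of 0.5 and factor-baseline correlation of 0.5, with no true modification. The rates at which the factor is flagged depend on which part of the baseline count it tracks:

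| The factor relates to | Change score, n=15 / n=24 | Baseline-adjusted, n=15 / n=24 |
|---|---|---|
| the measured baseline only, with no further link to the later count | 15% / 22% | 5% / 5% |
| the infant's stable load | 5% / 5% | about 22% / about 35% |

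Neither form is safe in both cases, and the documents do not show which case applies.

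**The case against.** The strongest reply has four parts.

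1. The final paragraph of 6.3.3 never says treated infants only. The restriction is inferred from Table 7, and the objectives and culture schedule point the other way. The general text of 6.3.3 also plans unpaired comparisons between cohorts. This stands: the firm finding is an unnamed population and a table entry that conflicts with other sections. Even if untreated infants were included, though, no cohort-by-factor comparison is named.

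2. The paragraph names no test or selection rule and does not use the word response. This also stands. The percentages above describe a 5% test that someone might apply, not a rule in the plan. The word comes from the cytokine row, where the analyses are only to be considered.

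3. The work is labelled hypothesis generating, and later randomised trials can test interactions properly. This limits the harm to poorly chosen subgroups. No dose or safety decision depends on it.

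4. The contrast is imprecise, and families choose the cohort, so it can be confounded. This is correct, and it is why the contrast should not be a gate.

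A reader might go further and infer that any factor related to baseline load will be falsely flagged through regression to the mean, and that baseline adjustment is the cure. The documents do not support that. They specify no model and give no correlations, and step 4 shows that adjustment creates the error when the factor tracks stable load.

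**Conclusion.** The concern holds in limited form. With Table 7 as written, the analysis cannot distinguish a prognostic factor from a modifier of tobramycin's effect, although untreated data that bear on the question for three of the four factors are already to be collected. For assumed prognostic shifts of 0.5 to 1.0 SD, a treated-only 5% test would flag a factor unrelated to drug effect about 15-44% of the time (n=15) or 22-65% (n=24), against about 5% for the cohort-by-factor contrast. These rates rest on an evenly split binary factor and an equal shift in both cohorts; a smaller shift gives a smaller excess. Cytokines have no untreated measurements, so for them the ambiguity cannot be resolved in this study. The point merits correction because it is cheap to correct. It does not threaten the trial's primary purpose.

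**What to change.** - In Table 7, change the observational-cohort entry for CFU change to Yes, in line with the synopsis and sections 2.2, 5.1.4.3 and 5.3.
- In the last paragraph of 6.3.3, name the population. For organism (grouped, for example *P. aeruginosa* versus other, since section 3.4.3 lists seven entries), RSS and mechanics, run the analysis in both cohorts. Report the cohort-by-factor difference with its 95% CI beside the treated-only result.
- Describe treated-only associations, including all cytokine results and the cluster and discriminant analyses, as predictors of CFU change and not of response to tobramycin.
- Show results with and without baseline log10 CFU as a sensitivity analysis, and state that either form can mislead, depending on whether the factor tracks transient or stable load.

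The cost is wording and a modest amount of extra analysis; no new samples are needed. The contrast will be wide (about 1.6 to 2.2 SD detectable at 80% power) and open to confounding. It should therefore inform interpretation, and a candidate subgroup may still be named on other grounds.

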6.3.4 Pharmacokinetic analysis

Patient specific pharmacokinetic parameters will be calculated using log-linear regression as the equation: $K_{el} = (ln Cp_{max}/Cp_{min}) / t$, where K_{el} is the elimination rate constant from plasma, Cp_{max} and Cp_{min} and the peak and trough concentrations, respectively, and t is the time between samples. Based on this equation, the estimated concentration at the time of tracheal aspirate sampling can also be calculated. The correlation between tracheal and plasma tobramycin concentrations will then be determined.

Population pharmacokinetic (PK) analysis will be conducted using nonlinear mixed effects modeling with the program NONMEM (Icon Inc.). Dosing information and plasma tobramycin concentrations will be used to facilitate model development. Mean population PK parameters (clearance, volume of distribution) will be estimated using the first-order conditional estimation with interaction method. A 2-compartment model with first order absorption will be utilized based on prior knowledge of inhaled tobramycin.²¹ Between subject variability and covariate effects (body weight, PMA, renal function, sex) will be

assessed. Owing to a lack of existing data on the likely plasma tobramycin levels after inhalational administration in the target population, it is uncertain whether the sampling strategy implemented in this trial will enable formal population PK analysis. Therefore, this analysis will be conducted strictly as an exploratory aim.

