Safety Evaluations	The primary study endpoint of the phase 1 trial is a safety outcome defined as the occurrence of any of the following:							
	 Trough serum tobramycin level (measured 11 hours after the last administered dose) ≥1µg/mL Increase in serum creatinine level by ≥0.3mg/dL above the pretrial level Increase in serum creatinine >1.5-fold above the pre-trial level Urine output <0.5mL/kg/hr for 12 hours Any serious adverse event possibly attributable to the study drug 							
	 Additional exploratory secondary safety endpoints are: New onset or worsened coughing associated with a change in respiratory status (SpO₂ <80% for >10 seconds; need for increase in FiO₂ by >20%) Obstruction of the endotracheal tube requiring tube replacement 							
	 Unplanned tracheal extubation Desaturation (SpO₂ <80% for >10 seconds) during administration of inhaled tobramycin Rates of pre-discharge failed audiology examinations Rates of new intra-patient microbial resistance to tobramycin 							
Efficacy Evaluations	 The exploratory secondary efficacy endpoints are: Tracheal aspirate tobramycin levels Change in tracheal aspirate pathogenic bacterial colony forming unit (CFU) counts measured by high resolution, quantitative 							
	 culture Change in the following measures of administered respiratory support: fraction of inspired oxygen (FiO₂), ventilator mean airway pressure (MAP), respiratory severity score (FiO₂ x MAP) Change in the following measures of hypoxemia (SpO₂<80%): Intermittent hypoxemia (events lasting 10s-3min), prolonged hypoxemia (events lasting >1min), and daily proportion of time in 							
	 hypoxemia Change in tracheal aspirate cytokine levels, neutrophil/WBC ratio, and patterns in the airway microbiome Change in dynamic lung compliance and airway resistance 							

Pharmacokinetic Evaluations	Blood and tracheal aspirate samples for pharmacokinetic (PK) analyses will be collected. Patient specific PK parameters will be calculated using log-linear regression based on plasma peak and trough tobramycin concentrations.
	Population PK analyses will be conducted using nonlinear mixed effects modeling. Mean population PK parameters (clearance, volume of distribution) will be estimated using the first-order conditional estimation with interaction method. A 2-compartment model with first order absorption will be utilized based on prior knowledge of inhaled tobramycin pharmacokinetics.

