In a separate study, Rosenfeld et al. found that peak serum concentrations occurred approximately 1 hour (range 0.5-2hr) after administration of 300mg of tobramycin solution for inhalation to children aged 0.6-5.8 years (**Figure 5**).²⁶ The average peak serum concentration of 0.6μ g/mL (range: <0.2 to 1.2μ g/mL) was within the acceptable, safe trough range for intravenous tobramycin. Serum tobramycin levels reached negligible values in most study patients within 4 hours after administration (**Figure 5**).²⁶

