^a "Day 0" procedures to be completed ≤7 days prior to administration of the first study drug dose. The quantitative tracheal aspirate culture and cell count differential obtained during the screening phase will be used for the laboratory values. Prior to initiating study drug therapy, one additional tracheal aspirate will be collected for cytokine level measurements and 16s sequencing.

^b "Day 15" procedures to be completed ≤48 hours after administration of the last study drug dose

° Follow-up tracheal aspirate for quantitative culture will be collected 14 days after the last administered dose of inhaled tobramycin or on the day of planned tracheal extubation if earlier

^d Tracheal aspirate for tobramycin level measurements obtained on trial day 7 will be collected approximately 1hr, 3hr, 6hr, 9hr, and 11hr after drug administration. Samples collected on trial days 4, 10, and 14 will be collected approximately 11hr after administration of doses number 8, 20 and 28, respectively.

e Serum and blood tobramycin trough levels will be drawn concurrently, 11 hours after administration of the previous dose

^f Blood draws for comprehensive metabolic panels should be bundled with draws for tobramycin trough levels or other clinically ordered blood draws. Comprehensive panel to include a magnesium and phosphorus level on day 7 and 14.

^g Serum and blood tobramycin peak levels will be drawn concurrently, 1 hour after completion of the previous dose

^h Up to 6 blood tobramycin levels per infant will be drawn concurrent with clinically ordered blood draws.

ⁱ Weekly medical record review to assess for adverse events will take place until hospital discharge

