5.1.5.2 Blood Sampling for Pharmacokinetic Analyses

Blood (0.2mL) will be collected for pharmacokinetic analyses at 2 set time points on day 7 plus up to 6 random collections coincident with clinically obtained draws. The lower limit of quantification for serum tobramycin concentrations in the CHOP clinical laboratory is 0.6 µg/mL. Based on this quantification limit, we anticipate that the majority of subjects will have clinically undetectable trough and/or peak levels, limiting the ability to characterize serum pharmacokinetics. Measurement of blood plasma tobramycin levels will be performed at the University of Florida College of Pharmacy using high-performance liquid chromatography tandem mass spectrometry (HPLC-MS/MS). This will enable quantification of drug levels down to a level of 50-100 ng/mL and facilitate estimation of patient-specific pharmacokinetics. Individually identifiable will be removed from samples and the samples will be labeled with unique identifiers. The CHOP study team will be able to link the unique identifiers to individually identifiable information, but the individually identifiable information will not be available to outside researchers.

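### Individual K_el rests on one plasma peak and one 11 h trough, with no rule for values below the HPLC-MS/MS limit, which are likely at the lower doses

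*Combined protocol and SAP*

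**What the plan says.** Section 6.3.4 states: "Patient specific pharmacokinetic parameters will be calculated using log-linear regression as the equation" K_el = ln(Cp_max/Cp_min)/t. The word regression might suggest several points per infant, but the printed equation takes two concentrations, and the synopsis (Pharmacokinetic Evaluations) says the parameters are "based on plasma peak and trough tobramycin concentrations".

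The footnotes to Table 5 (Section 4.3.1) fix the times: "Serum and blood tobramycin peak levels will be drawn concurrently, 1 hour after completion of the previous dose", and "Serum and blood tobramycin trough levels will be drawn concurrently, 11 hours after administration of the previous dose". Section 5.1.5.2 places the two scheduled PK samples on day 7. The same footnotes add: "Up to 6 blood tobramycin levels per infant will be drawn concurrent with clinically ordered blood draws". Those random samples do not enter the two-point formula.

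Section 5.1.5.2 describes two assays. The clinical assay quantifies down to 0.6 µg/mL. HPLC-MS/MS is used for the plasma PK samples: "This will enable quantification of drug levels down to a level of 50-100 ng/mL".

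Section 6.3.4 then uses the fitted line to estimate plasma concentration at the times of tracheal sampling and correlates the two. Its caveat about feasibility covers the population model only. No section says how a plasma value below the HPLC-MS/MS limit is handled, or what is reported for an infant without a calculable K_el.

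**The concern.** With Cp_min below the limit, K_el cannot be calculated. Two informal remedies are common, and both err in the same direction. Dropping the infant keeps those who eliminate slowly. Setting the trough to the limit makes Cp_min too high and K_el too low. Either way half-life is overstated. Because peaks fall with dose, the lower doses suffer more.

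At stake are the secondary objective that relates dose to plasma pharmacokinetics (Section 2.2) and the tracheal-plasma correlation, which inherits any error in K_el. The protocol's background points to low troughs. For young children given 300 mg, Section 1.6.1 reports: "Serum tobramycin levels reached negligible values in most study patients within 4 hours after administration". Section 1.7 expects no detectable trough at 78 mg, without naming an assay.

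**Working it through.** **Inputs from the documents.** Mean peak 0.6 µg/mL at 300 mg, range <0.2 to 1.2 (Section 1.6.1). Maximum peaks by dose (Table 4). HPLC-MS/MS limit (LLOQ) 0.05-0.10 µg/mL (Section 5.1.5.2). Sampling at 1 h and 11 h, so t is about 10 h (nebulization time ignored). At most 6 infants per level, 24 in all (Section 3.3.2). In one young-child trial at 300 mg, peak 1.0 ± 0.4 and trough 0.4 ± 0.5 µg/mL (Table 3).

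**Step 1: the plan's own figures.** Table 4 peak = 1.2 × dose/300 gives 0.312, 0.600, 0.864 and 1.200 µg/mL. IV equivalent = 2 × 10 × peak/26.0 gives 0.240, 0.462, 0.665 and 0.923 mg/kg/day. Both agree with Table 4 to rounding. The documents give no figure for K_el, half-life or the share of measurable troughs.

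**Step 2: half-life needed for a measurable trough** = 10 × ln 2 / ln(peak/LLOQ). At 78 mg the scaled mean peak is 0.6 × 78/300 = 0.156. The result is 6.931/ln(3.12) = 6.1 h at LLOQ 0.05, and 6.931/ln(1.56) = 15.6 h at 0.10.

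| Dose | Mean peak scaled, LLOQ 0.05 / 0.10 | Table 4 maximum peak, LLOQ 0.05 / 0.10 |
|---|---|---|
| 78 mg | 6.1 / 15.6 h | 3.8 / 6.1 h |
| 150 mg | 3.9 / 6.3 h | 2.8 / 3.9 h |
| 216 mg | 3.2 / 4.7 h | 2.4 / 3.2 h |
| 300 mg | 2.8 / 3.9 h | 2.2 / 2.8 h |

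Each entry is also the half-life assigned to an infant with that peak if a below-limit trough is set to the limit, whatever the true value.

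**Step 3: what half-life do the sources imply?** The Table 3 means give 10 × ln 2 / ln(1.0/0.4) = 7.6 h. If negligible at 4 h in Section 1.6.1 is read as below 0.2 µg/mL (an assumption), a 0.6 peak at 1 h implies less than 3 × ln 2 / ln(0.6/0.2) = 1.9 h. The size must therefore be shown over a range.

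**Step 4: selection if infants without a trough are dropped.** Simulation assumptions: lognormal half-life and peak, each with CV 40%, independent, peak proportional to dose, half-life not depending on dose. Cells give the share usable and the overstatement of median half-life among those infants.

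| True median half-life (mean 300 mg peak) | 78 mg, LLOQ 0.05 | 78 mg, LLOQ 0.10 | 300 mg, LLOQ 0.05 | 300 mg, LLOQ 0.10 |
|---|---|---|---|---|
| 2 h (0.6) | 1%, ×2.44 | <1%, ×3.01 | 19%, ×1.64 | 5%, ×1.99 |
| 3 h (0.6) | 5%, ×1.86 | <1%, ×2.33 | 53%, ×1.27 | 24%, ×1.52 |
| 4 h (0.6) | 15%, ×1.57 | 1%, ×1.95 | 77%, ×1.11 | 47%, ×1.29 |
| 6 h (0.6) | 41%, ×1.28 | 6%, ×1.58 | 96%, ×1.02 | 80%, ×1.10 |
| 8 h (1.0) | 89%, ×1.05 | 48%, ×1.21 | 100%, ×1.00 | 98%, ×1.01 |

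**Step 5: carry-over to the tracheal correlation.** Take a peak of 0.156 µg/mL and an assumed half-life of 4 h. At 6 h (5 h after the peak) plasma is 0.156 × 2^(-5/4) = 0.066. With the trough set to the limit, the line gives √(0.156 × 0.05) = 0.088 or √(0.156 × 0.10) = 0.125, about 1.3 to 1.9 times too high.

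**Step 6: does censoring help?** In simulated trials of 24 infants (6 per dose, mean 300 mg peak 0.6), a lognormal likelihood treated below-limit troughs as upper bounds on half-life.

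| True half-life, LLOQ | Complete-case | Censored fit |
|---|---|---|
| 3 h, 0.05 | 4.1 h | 3.05 h |
| 4 h, 0.10 | 5.6 h | 4.0 h |
| 6 h, 0.10 | 7.1 h | 5.9 h |

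At 2 h and 0.10, about 0.5 of 24 infants had a usable trough and neither method worked. This is a simpler model than NONMEM and uses no random samples.

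**The case against.** A reader might infer that the protocol itself expects most infants to lack a usable trough for this calculation. It does say "we anticipate that the majority of subjects will have clinically undetectable trough and/or peak levels". But that sentence, like Section 5.4, concerns the clinical assay at 0.6 µg/mL. HPLC-MS/MS is 6 to 12 times more sensitive and was added for this reason. No section says that most troughs fall below its limit, so the stronger reading is not supported.

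Nor do the documents support saying that half-life will be overstated. The plan specifies neither dropping nor substituting values. The Table 3 means imply almost no bias at 300 mg. They do not clear the lowest dose, however, because the trough SD exceeds its mean. With a lognormal or gamma shape on those moments (assumed), 5-32% of troughs fall below 0.05-0.10 µg/mL at 300 mg, and 39-67% do so when scaled to 78 mg.

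A spurious dose trend is also not shown at this size. At a true 4 h, 1-15% of 6 infants is 0.06 to 0.9 infants with an estimate at 78 mg. A visible gap there is more likely than a misleading trend.

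Finally, the pharmacokinetic objectives are exploratory, and dose escalation uses the clinical-laboratory trough against 1 µg/mL, not K_el. That stands and limits the weight of the point.

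**Conclusion.** The gap is real: a two-point formula, one plasma trough per infant, no rule below the limit, and random samples left out of the individual estimate. The direction of error under either informal remedy is certain, and it is worst at the lowest dose.

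The size is conditional on the true half-life. At about 3-4 h, complete-case half-life would be overstated 1.6 to 2.3 times at 78 mg and 1.1 to 1.5 times at 300 mg. At about 7-8 h the bias at 300 mg is near nil, with some left at 78 mg. At about 2 h or less, the problem is that few infants at any dose have an estimate.

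These figures rest on dose-proportional peaks, the assumed CVs, independence of peak and half-life, and t = 10 h. This is an inexpensive improvement to an exploratory analysis, and no safety decision depends on it.

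**What to change.** In Section 6.3.4, state that plasma values below the HPLC-MS/MS limit are treated as left-censored. Fit the peak, trough and random samples together in the planned NONMEM model with a censored likelihood (the M3 method). Take individual K_el, and the plasma concentrations for the tracheal correlation, from that model.

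If the model is not estimable, report the bound K_el > ln(Cp_max/LLOQ)/t for each infant with a quantifiable peak and a censored trough. Where the peak is also below the limit, report K_el as not estimable. With an assumed peak CV of 50%, that would be 1.5-24% of infants at 78 mg.

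Report the share below the limit by dose, and state that a dose trend in complete-case half-life will not be interpreted.

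The cost is a few lines of SAP text and modest extra modelling. No sample or software is added. The model may not converge with at most 24 infants, which is why the fallback should be written in advance.
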